# 1. Glossary

AE	Adverse Event
CRF	Case Report Form
DAMP	damage-associated molecular pattern
DAWN	Disabilities and wellness network
EC	Endothelial cell
ECBx	Endothelial cell biopsy
GCP	Good Clinical Practice
HTA	Human Tissues Act
ICF	Informed Consent Form
ICH	International Conference on Harmonisation
ICU	Intensive care unit
ISF	Investigator Site File
РАМР	pathogen-associated molecular pattern
PI	Principal Investigator
R&D	Research, Development and Innovation department
REC	Research ethics committee
RNA	Ribonucleic acid
RSFT	Royal Surrey NHS Foundation Trust
SAE	Serious Adverse Event
SOP	Standard Operating Procedure
SUSAR	Suspected Unexpected Serious Adverse Reaction
TMF	Trial Master File
UOS	University of Surrey

## 3. Protocol Summary

Title	Characterization of endothelial cells in multiple inflammatory pathologies			
Short title	JEDI-2			
Sponsor	Royal Surrey NHS Foundation Trust			
Design	Prospective observational study of three cohorts: i) healthy volunteers, ii) surgical patients, iii) critically ill patients.			
Primary objectives	To identify the changes in mRNA expression in endothelial cells from surgical patients and sepsis patients			
Secondary objectives	Stratification of patients based on mRNA expression from endothelial cells.			
	Characterisation of microparticles, histones and cell free DNA.			
Target accrual	Part 1: 25 healthy volunteers, 20 patients with sepsis and 20 elective abdominal surgery			
	Part 2: 20 patients with sepsis and 20 elective abdominal surgery			
Inclusion criteria (both parts)	
 
≥18 Years old
 
At RSFT for either and emergency admission to ICU, an elective surgery or as a healthy volunteer.
 
			
Exclusion criteria (both parts)	
 
Prisoners
 
Anticipated prohibitively difficult venous cannulation
 
Presenting with inflammatory diseases and disorders including but not limited to arthritis, peripheral artery disease, vasculitis, diabetes with end organ damage, cardiovascular disease and CKD.
 
Currently prescribed immunomodulatory medication or immunocompromised
 
Received chemotherapy within 2 weeks of predicted sampling.
 
History of recent trauma
 
			
Number of sites	1			
Duration of recruitment	12-18 months			
Duration of patient follow-up	Up to 28 days			
Definition of end of trial	End of follow-up of last patient			

#### 4. Lay summary

The immune system is a complex network of cells and molecules that protects the body from infection and injury. When the immune system is activated, it produces inflammation, which is a natural response to help heal the body. However, too much inflammation can be harmful and lead to serious complications, such as sepsis, low blood pressure, organ failure and death.

The interaction of cells that line the blood vessels (endothelial cells, EC) with the immune system, is believed to be the root cause of these symptoms. When exposed to inflammation, the instructional molecules (RNA) inside the EC change. This leads to a change of operation promoting the severe symptoms previously mentioned.

Researchers have developed new safe techniques to collect these cells from the blood vessels of patients to study disorders like diabetes, heart disease and stroke. This technique involves gently inserting a metal guidewire into an arm vein to collect ECs.

This study plans to collect ECs from patients undergoing surgery or admitted to intensive care. We also plan to collect control samples from healthy volunteers. Samples will be collected over the duration of the patients to RSFT. The RNA will be removed from the cells and counted to highlight changes in instructions in the cells.

Data from this study will potentially highlight new pathways involved in inflammation and help classify how some patients will react to current treatments. To obtain this data, this study will be split into 2 parts. Part 1 focuses on collecting one sample from a patient when they are at their most unwell states and comparing that to a sample from a healthy person. Part 2 will focus on key mRNA molecules identified during Part 1 and identifying how their expression changes over time.

#### 5. Background

**The immune response** is a complex process that is essential for protecting the body from infection and orchestrating the repair of injured tissues. Activation can be caused by severe infection (sepsis), or from significant injury to tissues - such as occurs during major surgery, trauma, pancreatitis or burns(1,2).

**Pattern recognition receptors**. The innate immune response can be triggered through pattern recognition receptors. In infection, these receptors detect pathogen-associated molecular patterns (PAMPs)(3) and in sterile tissue injury, damage-associated molecular patterns (DAMPs)(4). Profound activation can cause systemic inflammation and, if excessive, may be harmful.

**Sepsis and surgery.** Sepsis is a dysregulated immune response to infection and is the most studied cause of systemic inflammation. It can be difficult to study due to its unpredictable nature and the uncertainty of defining the onset of infection(5). Planned major surgery causes similar systemic inflammation and many of its characteristic manifestations. Improving patients' outcomes from surgery is important to study in itself, but surgery is also a good model for studying sepsis – with known time of onset and a predictable evolution (2).

**The endothelium** is a single layer of cells that lines the inside of blood vessels. It is constantly exposed to a variety of stimuli, including blood flow, shear stress, and inflammatory mediators, and it responds to these stimuli by secreting a variety of factors that regulate vascular tone, coagulation, and inflammation. It is also a selectively permeable barrier between the extravascular and intravascular compartments and can alter its permeability acutely(6–8). Altered endothelial cell (EC) function has predominantly been studied in chronic diseases (9,10) but is implicated in acute life-threatening conditions including sepsis and acute respiratory failure (for example, from COVID or other respiratory infections). Figure 1 shows our concept that ties injury to alterations in EC function and how this is clinically manifest.

Figure 1: Conceptualised relationship between triggers of systemic inflammation, the immune response, the endothelial response, and the clinical features.

**New method** – **EC biopsy (ECBx).** Researchers studying endothelial dysfunction in humans have access to a range of commercially available cells for in vitro studies, but there are substantial limitations to their use. Unprecedented insights could be gained from serial sampling of ECs from individuals with acute conditions. The first successful attempt to obtain ECs from patients was reported in 1999 by Feng et al (11). Their technique involved inserting a stainless-steel J-shaped guidewires into major vessels and collecting the tissue adherent to the guidewire. The technique has evolved into using other vascular implements such as endovascular coils and stents to study the effects of diverse diseases (10,12). Believing that ECs from patients would offer improved insights into the vascular alterations that take place during systemic inflammation, we performed a pilot study (IRAS 310961).

We assessed the feasibility of ECBx in a surgical and intensive care setting. Discarded guidewires used during arterial and central line placements were collected from both surgical (n=16) and intensive care (n=16) patients. We also collected an additional biopsy from a peripheral arm vein in surgical patients only. ECs were then isolated from the guidewires and analysed using flow cytometry for absolute cell counts. From arterial lines we recovered an average of 536; from central lines we recovered an average of 598; from peripheral cannulation we obtained 736. One sample had RNA isolated which yielded a total

of 105ng of material. We also assessed the tolerability of the ECBx through collection of adverse event (AE) data and a short questionnaire. There were no serious AEs related to ECBx, with only four patients (25%) of patients experiencing minor bruising which resolved without any complication. Patient feedback from the pilot study was overwhelmingly positive. All said that the biopsy was bearable and they could tolerate additional ECBx (mean of 3 additional biopsies).

**Biomarkers of EC function**. It is not possible to directly measure the functions of the endothelium in patients but there are methods to gain insights. i) circulating levels of proteins reflect some aspects of EC function such as von Willebrand factor(13), Angiopoietin2(14) and angiotensin 2(15) ii) changes in circulating leukocytes (leukocytosis or leukopenia)(16) iii) micro particles released from EC can have pro-inflammatory, pro-thrombotic and vasoregulatory properties and also contain microRNAs (miRNAs), non-coding RNA molecules regulating genes (17,18) iv) circulating miRNA (19) V) measuring aspects of EC structure and function, including flow cytometry.

**RNA sequencing of EC.** We will process our patient-sourced ECs to preserve the mRNA for subsequent analysis. These analyses will provide insight into the EC function at the time of acquisition. RNA sequencing provides very detailed information about the relative abundance of many different transcripts. We can use knowledge of which transcripts are involved in which molecular pathways (for example a pro-inflammatory pathway like NF $\kappa$ B) to understand how putative pathways are expressed. Comparison of pathway expression between times within patient cohorts and between patient cohorts will allow us to see how EC respond in patients related to their clinical status.

**Hospital.** The Royal Surrey hospital intensive care unit (ICU) receives >600 patients per year who have had major surgery that typically has been prolonged (>6 hours) and often associated with major tissue injury and blood loss (~1L). These patients have systemic inflammation and the predominant feature of altered EC function is loss of vasomotor tone causing hypotension. This is a major reason why they are managed on the ICU where we have specific expertise in treating hypotension. As an acute hospital we also regularly treat patients with severe infections and admit >300 patients/y with sepsis to the ICU. These patients will invariably have features of systemic inflammation and altered EC function.

#### **Research question**

Using the ECBx technique, our research question is: "In patients with sepsis or following major surgery, are changes in EC expression of putative pathways related to the clinical manifestations of SI?"

#### Aims

To determine the relationship between changes in EC expression in putative pathways, and the clinical manifestations and patient outcome for patients with sepsis or following major surgery.

To identify the implicated pathways which will be useful to develop novel personalised therapies that may improve patient outcome.

#### **Objectives for Part 1**

- Recruit a cohort of healthy volunteers for method validation purposes. Undertake ECBx procedure (peripheral vein) to:
  - Optimise methodology for RNA extraction
  - Use as a control to compare with the patient groups.
- Use a small number of these samples to develop methods of cell culture.
- Concurrently recruit two patient cohorts: (A) planned major surgery, (B) acutely critically unwell patients (recently admitted to ICU with sepsis).
- For each:
  - Undertake one ECBx procedure (peripheral vein). Isolate EC from guidewire. RNA sequencing on EC. In accordance with the corresponding schedule of events.
  - Characterise clinical status of the cohorts for example extent of vasodilation as reflected in the dose of vasopressor drug being delivered to maintain an adequate blood pressure.
  - Characterisation of blood sample specifically microparticles, histones and cell free DNA, leukocyte activity.
- Analyse RNA data to identify candidate gene expression changes that are linked to the change in phenotype

#### **Objectives for Part 2**

- Recruit a second cohort of patients with (a) sepsis and (b)those undergoing major abdominal surgery.
- For each:
  - Undertake serial ECBx procedure (peripheral vein). Isolate EC from guidewire. RNA sequencing on EC. In accordance with the corresponding schedule of events.
  - Characterise clinical status of the cohorts for example extent of vasodilation as reflected in the dose of vasopressor drug being delivered to maintain an adequate blood pressure.
  - Characterisation of blood sample specifically microparticles, histones and cell free DNA, leukocyte activity.
- Use data from Part 1 to characterise the change in candidate gene expression.

### 6. Trial design

This is a two-part prospective observational cohort study comparing the mRNA changes in EC from two independent biological onsets.

Part 1 focuses on identification of mRNA expression changes in one timepoint of acutely inflamed patients in comparison to a healthy control.

Part 2 focuses on validating data from Part 1 in the same patient groups by analysing mRNA over several timepoints.

Part 2 will commence upon completion of the Part 1 data review. See section 9 for further details.

#### 6.1. Study procedures

#### Part 1, Cohort 1: Healthy volunteers

	Screening	Sample	7-days Post sample
Consent 	Х		
Demographics 	Х		
Medical history 	Х		
ECBx 		Х	
Blood sampling 		Х	
AE and SAE monitoring 	Х	Х	Х

1 - Consent must be performed to any study procedures. A standard consent or deferred consent model will be used, see section 7.9 for further details

2 – Medical history and demographics will be collected from the available medical records on Surrey Safe Care and NHS SPINE

3 – Severity of illness and clinical characterisation will use standardised methods such as qSOFA score and data from patient record to define. See section 7.16 for further details

4 - Both samples to be collected at the same time. See section 7.15 for further details

5 – See section 9 for further detail

	Screening	24 hours post- surgery	48 hours post- surgery	28-day follow- up
Consent 	x			
Demographics 	Х			
Medical history 	Х			
Severity of illness scoring 	Х	Х	Х	
ECBx 		Х		
Blood sampling 		Х		
Clinical characterisation 		х	х	
AE and SAE monitoring 	Х	x	Х	Х
Survival outcome				Х

#### Part 1, Cohort 2: Surgical cohort

1 - Consent must be performed to any study procedures. A standard consent or deferred consent model will be used, see section 7.9 for further details

2 – Medical history and demographics will be collected from the available medical records on Surrey Safe Care and NHS SPINE

3 – Severity of illness and clinical characterisation will use standardised methods such as qSOFA score and data from patient record to define. See section 7.16 for further details

4 - Both samples to be collected at the same time. See section 7.15 for further details

5 – See section 9 for further detail

#### Part 1, Cohort 3: Sepsis cohort

	Screening	On admission	24 hours post admission	48 hours post admission	28-day follow-up
Consent 	Х				
Demographics 	Х				
Medical history 	Х				
Severity of illness scoring 		X	Х	Х	
ECBx 		X			
Blood sampling 		X			
Clinical characterisation 			X	X	
AE and SAE monitoring 	Х	X	Х	Х	Х
Survival outcome					Х

1 - Consent must be performed to any study procedures. A standard consent or deferred consent model will be used, see section 7.9 for further details

2 – Medical history and demographics will be collected from the available medical records on Surrey Safe Care and NHS SPINE

3 – Severity of illness and clinical characterisation will use standardised methods such as qSOFA score and data from patient record to define. See section 7.16 for further details

4 - Both samples to be collected at the same time. See section 7.15 for further details

5 – See section 9 for further detail

#### Part 2, Cohort 1: Surgical cohort

	Screening	Pre-surgery	24 hours post- surgery *	48 hours post- surgery *	28-day follow- up
Consent 	Х				
Demographics 	Х				
Medical history 	Х				
Severity of illness scoring 	Х		Х	Х	
ECBx 		Х	Х	Х	
Blood sampling 		Х	Х	Х	
Clinical characterisation 		Х	Х	Х	
AE and SAE monitoring 	Х	Х	Х	Х	Х
Survival outcome					Х

1 - Consent must be performed to any study procedures. A standard consent or deferred consent model will be used, see section 7.9 for further details

2 – Medical history and demographics will be collected from the available medical records on Surrey Safe Care and NHS SPINE

3 – Severity of illness and clinical characterisation will use standardised methods such as qSOFA score and data from patient record to define. See section 7.16 for further details

4 - Both samples to be collected at the same time. See section 7.15 for further details

5 – See section 9 for further detail

\*Time and procedures subject to changed based on emerging data from part 1. See section 8 for further details

#### Part 2, Cohort 2: Sepsis cohort

	Screening	On admission*	24 hours post admission *	48 hours post admission *	28-day follow-up
Consent 	Х				
Demographics 	Х				
Medical history 	Х				
Severity of illness scoring 		х	Х	Х	
ECBx 		х	Х	Х	
Blood sampling 		x	Х	X	
Clinical characterisation 			Х	X	
AE and SAE monitoring5	Х	X	Х	Х	Х
Survival outcome					Х

1 - Consent must be performed to any study procedures. A standard consent or deferred consent model will be used, see section 7.9 for further details

2 – Medical history and demographics will be collected from the available medical records on Surrey Safe Care and NHS SPINE

3 – Severity of illness and clinical characterisation will use standardised methods such as qSOFA score and data from patient record to define. See section 7.16 for further details

4 - Both samples to be collected at the same time. See section 7.15 for further details

5 – See section 9 for further detail

\*Time and procedures subject to changed based on emerging data from part 1. See section 8 for further details

Figure 1: overview of the planned study. Part 1 – comparsion of an EC mRNA from 2 cohorts of patients taken at peak inflamation vs a healthy control. Data from this part will be reviewed to determine time points and genes of interest(see section 8 for further details). Part 2 - serial sampling looking at changes in gene expression from the genes of interest identified in Part 1.

Figure 3: Schematic of major events for patients having planned major surgery. \*Predicted time points for part 2 only.

Figure 4: Schematic of major events for patients admitted to ICU with sepsis. \*Predicted time points for part 2 only. \*\*if required

### 7. Eligibility criteria

Eligibility criteria will be the same for both cohorts of patients in Part 1 and 2. Healthy volunteers eligibility criteria only applicable to Part 1.

### 7.1. Inclusion – Healthy volunteer

- Adult ≥ 18 years
- Able and willing to give consent

#### 7.2. Exclusion – healthy volunteer

- Not currently a patient within the hospital
- Absence of inflammatory diseases and disorders including but not limited to arthritis, peripheral artery disease, vasculitis, diabetes, cardiovascular disease and CKD.
- Not on immunomodulatory medications, such as corticosteroids

- History of recent major trauma within the last 2 months (e.g., surgery or injury requiring hospitalisation)
- •

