## 13.3. Protocol compliance

Prospective, planned deviations or waivers to the protocol are not allowed must not be used e.g. It is not acceptable to enrol a participant if they do not meet the eligibility criteria or restrictions specified in the trial protocol

Accidental protocol deviations can happen at any time. They must be adequately documented on the relevant forms and reported to the Chief Investigator and Sponsor immediately. Frequent deviations from the same root cause will be investigated to limit the effect it has on any data collected.

Minor protocol deviations are attributed to events that have minimal impact on the data set. These include but are not limited too samples being taken outside of specified nominal timepoint, a non-delegated individual performing a task they are not assigned and variance in sampling depth.

Major deviations are attributed to events that have a measurable impact on the data set and may necessitate a replacement participant. These include but are not limited too, enrolling a patient that is not eligible for the study, delayed transfer of sample to analytical laboratory and incorrect handling of sample in analytical laboratory.

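### Three of the four healthy-volunteer exclusion criteria in Section 7.2 are worded backwards, so the text as written bars healthy people from the control group

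*Protocol*

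**What the plan says.** Section 7.2 of the protocol carries the heading "7.2. Exclusion – healthy volunteer", and the table of contents repeats it as an exclusion section. It has four entries with content:

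1. "Not currently a patient within the hospital"
2. "Absence of inflammatory diseases and disorders including but not limited to arthritis, peripheral artery disease, vasculitis, diabetes, cardiovascular disease and CKD"
3. "Not on immunomodulatory medications, such as corticosteroids"
4. "History of recent major trauma within the last 2 months (e.g., surgery or injury requiring hospitalisation" (closing bracket omitted here)

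Section 7.1, the matching inclusion list, has two entries: adult age and "Able and willing to give consent".

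The summary in Section 3 gives exclusions for both parts, beside an inclusion line that names healthy volunteers. There the disease criterion runs the other way: "Presenting with inflammatory diseases and disorders including but not limited to arthritis, peripheral artery disease, vasculitis", followed by further conditions. Section 13.3 rules out waivers: "It is not acceptable to enrol a participant if they do not meet the eligibility criteria or restrictions specified in the trial protocol". It also lists enrolment of an ineligible patient among the major deviations that may call for a replacement participant.

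**The concern.** An exclusion criterion removes a person when the statement is true of them. The first three entries in Section 7.2 are true of exactly the people the study needs as controls. The fourth is true of people it does not want. The list therefore mixes two directions, and neither *exclude if true* nor *exclude if false* works for all four.

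The volunteers are the healthy control against which Section 6 sets the acutely inflamed patients in Part 1. If their eligibility rule is reversed, staff cannot both follow the text and recruit a valid control group. A properly chosen volunteer is ineligible on paper, and one who satisfies the paper rule carries the disease and medication that the control group is meant to be free of.

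**Working it through.** No sample size or power figure is involved, so the check is one of logic.

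**Rule applied.** A person is eligible if every inclusion criterion is true and no exclusion criterion is true.

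**Direction of each Section 7.2 entry, read as an exclusion**

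| Entry | Who it removes as written | Direction |
|---|---|---|
| 1. Patient status | anyone who is not a hospital patient | reversed |
| 2. Inflammatory disease | anyone free of such disease | reversed |
| 3. Immunomodulators | anyone not taking them | reversed |
| 4. Recent major trauma | anyone with such trauma | correct |

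Reversed entries: 3 of 4.

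**Two test cases, both consenting adults**

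- *Healthy student, not a patient, no disease, no immunomodulator, no trauma.* Entries 1, 2 and 3 are true and entry 4 is false. Three exclusions are met, so the person is barred.
- *Hospital patient with inflammatory disease, on an immunomodulator, no recent trauma.* All four entries are false. No exclusion is met, so the person is eligible.

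The second profile is the only one that passes.

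**Does Section 7.1 repair this?** No. Age and consent say nothing about health.

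**Is it a house style?** No. Sections 7.4 and 7.6, the exclusion lists for surgical and critically ill patients, exclude when disease or immunomodulatory medication is present.

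**Combined with the summary.** If the Section 3 exclusions also apply to volunteers, nobody qualifies. The medication criterion alone shows this: Section 7.2 removes people not on immunomodulators, and Section 3 removes people who are prescribed them.

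**Against the stated purpose.** Section 7.7 wants controls without other conditions or medications that could confound the comparison. Section 7.9 draws them from hospital staff and volunteers and from university students, most of whom entry 1 would bar.

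**Extent.** Section 10.1 plans 25 volunteers, of whom 20 are analysed and 5 serve method validation. With 20 patients in each of two cohorts, Part 1 recruits 25 + 20 + 20 = 65 people, so the reversed rule governs 25/65 = 38% of them and the whole control group.

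**The case against.** The strongest reply is that nobody would be misled. The cohort is named for its health, Section 7.7 explains why, Section 7.9 limits the source to staff, volunteers and students, and the patient lists word the same items correctly. Each entry then has only one sensible reading, and the likely consequence is an audit query and not a contaminated control group. This stands as a limit on the probable harm. It does not make the rule correct, and the other safeguards are thin: a delegate may confirm eligibility (Section 7.9), volunteers give an oral history and their records are not consulted (Section 7.11), and data-quality checks end after the first patient or patients if those are satisfactory (Section 12).

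Three narrower points are also fair:

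- Section 7.17 classes as minor any deviation outside its own list of sample-handling failures. Under that section an ineligible enrolment would be minor, whereas Section 13.3 makes it major. The grade is therefore unsettled, but the ban on waivers is not.
- The background in Section 5 also foresees comparison between patient cohorts, which does not use the volunteers. The effect is confined to the two patient-versus-healthy contrasts.
- The summary is not simply the volunteer list turned round. It limits diabetes to cases with end organ damage, where Section 7.2 names diabetes without qualification. It adds prisoners, difficult cannulation and chemotherapy, and gives no time window for trauma. The intended volunteer rule therefore cannot be recovered just by deferring to the summary, which is a further reason to correct Section 7.2 itself.

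**Conclusion.** The point holds, and the text must be corrected. Three of the four volunteer exclusions are reversed. As written, Section 7.2 bars every healthy non-patient, and it conflicts with Sections 3, 7.7 and 7.9. It affects all 25 volunteers, including the 20 analysed as the only comparator for the surgical-versus-healthy and sepsis-versus-healthy contrasts.

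This is a drafting error with a clear intended meaning. The conclusion assumes only that an exclusion criterion removes a person when it is true. It does not assume that the wrong people have been or will be enrolled. No sample size, power or analysis figure changes.

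**What to change.** Either of two amendments resolves it:

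- move the first three entries of Section 7.2 to Section 7.1 as inclusion criteria; or
- keep them in Section 7.2 and turn them round: *currently a hospital patient*, *presence of inflammatory disease* (with the existing examples), and *taking immunomodulatory medication*.

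Recent major trauma stays in Section 7.2 under both options.

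The Section 3 summary should then state which of its exclusions apply to volunteers, and its diabetes and trauma wording should be reconciled with Section 7.2 so that the volunteer criteria are not altered by accident. Any eligibility checklist drawn from Section 7.2 should be corrected at the same time.

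The cost is one wording amendment, with no effect on recruitment targets or analysis.
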